### **2.3. Secondary Objectives /Endpoints**

- To evaluate and estimate the median duration of overall survival (OS) in Stage IIB-IIC melanoma patients.
- To evaluate and estimate the median duration of distant metastases-free survival (DMFS) in Stage IIB-IIC melanoma patients.
- To assess safety and toxicity using CTCAE V5.0

- To assess quality of life using the Functional Assessment of Cancer Therapy – Melanoma (FACT-M) quality of life instrument

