## **3. STUDY DESIGN**

### **3.1. Characteristics**

We will conduct a phase II single arm, multicenter clinical trial of adjuvant nivolumab in patients with resected American Joint Committee on Cancer stage IIB or IIC cutaneous melanoma (AJCC 8th edition).

Patients with new diagnosis of melanoma will be diagnosed and staged (including a negative sentinel lymph node biopsy or failed sentinel lymph node mapping) as per standard of care. Demonstration of lack of metastatic disease will be required prior to initiation protocol therapy. This can be via PET/CT or CT Scan of the Chest, Abdomen, and Pelvis. Patients with stage IIB and IIC melanoma will be identified and screened for eligibility within 6 months of the diagnosis. We will ask that patients consent to provide archived tumor material from the primary melanoma for the conduct of correlative studies.

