### **4.1. Eligibility Criteria**

#### **4.1.1. Inclusion Criteria**

1. Patients must have completely resected (as per standard of care) melanoma of cutaneous origin in order to be eligible for this study. Patients must be classified as Stage IIB or IIC cutaneous melanoma using the American Joint Committee on Cancer eighth edition. Patients with melanoma of mucosal or other non-cutaneous origin are not eligible. Patients with melanoma of ocular origin are not eligible.
2. Patients must have a negative sentinel lymph node biopsy or undergo a failed attempt at sentinel lymph node biopsy including lymphoscintigraphy which fails to show a sentinel lymph node from the melanoma primary site .
3. Patients must have systemic cross-sectional imaging (PET/CT or CT of chest, abdomen, and pelvis) which shows no evidence of metastatic disease.
4. Patient must be able to comprehend and sign a written informed consent and be willing to comply with all study procedures.
5. Men and women  $\geq 18$  years of age will be eligible.
6. Patients must have an ECOG performance status of 0 or 1.
7. Patients must have adequate bone marrow function as evidenced by all of the following: ANC  $\geq 1,500$  microliter (mcL); platelets  $\geq 100,000/\text{mcL}$ ; Hemoglobin  $\geq 10$  g/dL.
8. Patients must have adequate hepatic function as evidenced by the following: total bilirubin  $\leq 1.5 \times$  institutional upper limit of normal (IULN) (except Gilbert's Syndrome, who must have a total bilirubin  $< 3.0$  mg/dL), and SGOT (AST) and SGPT (ALT) and alkaline phosphatase  $\leq 2 \times$  IULN.
9. Patients must have adequate renal function as evidenced by ONE of the following: serum creatinine  $\leq 1.5 \times$  ULN OR measured or calculated creatinine clearance  $\geq 60$  mL/min.
10. Patients known to be HIV positive are eligible if they meet the following criteria within 30 days prior to registration: stable and adequate CD4 counts ( $\geq 350$  mm^3), and serum HIV viral load of  $< 25,000$  IU/ml. Patients may be on or off anti-viral therapy so long as they meet the CD4 count criteria.

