11. Women of childbearing potential must have a negative urine or serum pregnancy test within 28 days prior to registration. Women/men of reproductive potential must have agreed to use an effective contraceptive method for the course of the study through 120 days after the last dose of study medication. If a woman become pregnant or suspect she is pregnant while she or her partner is participating in this study, she must inform her treating physician immediately. A woman is considered to be of "reproductive potential" if she has had menses at any time in the preceding 12 consecutive months. In addition to routine contraceptive methods, "effective contraception" also includes heterosexual celibacy and surgery intended to prevent pregnancy (or with a side-effect of pregnancy prevention) defined as a hysterectomy, bilateral oophorectomy, or bilateral tubal ligation. However, if at any point a previously celibate patient chooses to become heterosexually active during the time period for use of contraceptive measures outlined in the protocol, he/she is responsible for beginning contraceptive measures. Patients must not be pregnant or nursing due to unknown teratogenic side effects
12. Therapy must be initiated within 120 days of surgical resection of the sentinel lymph nodes

and within 6 months of initial diagnosis.

13. Patients must be willing to have archived tumor specimens utilized for correlative studies if available.

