## **6. STUDY SCHEDULE**

### **6.1. Time and Events Schedule**

**Table 3.** Time and Events Schedule is on the following page.

	Screening	Treatment Cycle (4 Week Cycle) a												Follow up (months) k										End of Treatment (EOT)/Withdrawal m
														M1 Post-Scans	Every 3 months from last Infusion x 1 year				Every 6 months subsequently x2 years				Final Year	
															M3	M6	M9	M12	M18	M24	M30	M36	M42 and M48	
	28 Days*	1	2	3	4	5	6	7	8	9	10	11	12		M3	M6	M9	M12	M18	M24	M30	M36	M42 and M48	
Informed Consent	X																							
History and Physical Exam b	X	X	X	X	X	X	X	X	X	X	X	X	X	x	X	X	X	X	X	X	X	X	X	X
Vital Signs	X	X	X	X	X	X	X	X	X	X	X	X	X	X	X	X	X	X	X	X	X	X	X	X
Beta HCG Pregnancy Test c	X	X	X	X	X	X	X	X	X	X	X	X	X											
ECOG Performance Status	X	X	X	X	X	X	X	X	X	X	X	X	X	X	X	X	X	X	X	X	X	X	X	X
Laboratory Assessments d	X	X	X	X	X	X	X	X	X	X	X	X	X	X	X	X	X	X	X	X	X	X	X	X
Cross-sectional imaging, including at minimum chest, abdomen and pelvis e	X							X						X		X		X	X	X	X	X	X	X l
AE Assessment		Assessed at every visit																						
Research blood sample collection f	X j	X j			X			X			X			X		X		X	X	X				X
CTC Analysis g	X j	X j			X									X										
Quality of Life Assessment (Appendix #1)		X	X	X	X	X	X	X	X	X	X	X	X			X		X	X	X	X	X	X	X
Nivolumab Therapy		X	X	X	X	X	X	X	X	X	X	X	X											
Archived tissue request	X																							

\*Screening period is a total of 28 days; Screening labs that are performed within 7 days prior to C1D1 do not need to be repeated

a. Treatment may be administered with a window of ± 7 days.

b. Visits may be performed with a window of ± 14 days. Long-term follow up may be discontinued once the primary end point is assessed and met.

c. If female of childbearing potential, a pregnancy test will be required at screening visit and prior to the start of each cycle of study drug.

d. Laboratory Assessments:

- Hematology labs to include hemoglobin, hematocrit, red blood cell count, white blood cell count, platelets (direct platelet count), as well as total and differential CBC counts. The CBC differential includes enumeration of neutrophils, lymphocytes, eosinophils, monocytes, basophils and any abnormal blood cells noted in the differential.

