#### **9.1.2. Survival and Recurrence-free Survival**

Patients' survival times will be measured from the initial date of treatment to the recorded date of death. Recurrence-free survival (RFS) will be measured from the initial date of treatment to the date of documented recurrence. Distant Metastases-free survival (DMFS) is defined as the time from definitive surgery to the date of diagnosis of metastatic disease.

Overall survival and recurrence-free survival (RFS) will be estimated by the Kaplan-Meier method. The corresponding median survival times (with 90% confidence limits) will be determined, as will the cumulative percentage of patients remaining progression-free / alive at selected time points after initial treatment (e.g., 6, 12, and 18 months).

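### DMFS is timed from surgery although patients enter later and only with clear imaging, and death is not named as an event, so DMFS is biased upward

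*Combined protocol and SAP*

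**What the plan says.** DMFS is a secondary endpoint in the synopsis and in section 2.3: "To evaluate and estimate the median duration of distant metastases-free survival (DMFS) in Stage IIB-IIC melanoma patients". Its only definition is in section 9.1.2: "Distant Metastases-free survival (DMFS) is defined as the time from definitive surgery to the date of diagnosis of metastatic disease". The same section measures overall survival and RFS from the first treatment date. Section 2.2 defines RFS differently, from study registration to progression or death.

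Entry follows surgery and depends on being free of metastases:

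- Section 4.1.1, item 12: "Therapy must be initiated within 120 days of surgical resection of the sentinel lymph nodes" "and within 6 months of initial diagnosis".
- Section 4.1.1, item 3: "Patients must have systemic cross-sectional imaging (PET/CT or CT of chest, abdomen, and pelvis) which shows no evidence of metastatic disease".
- Section 3.1: "Demonstration of lack of metastatic disease will be required prior to initiation protocol therapy".
- Section 6.1, Table 3, marks cross-sectional imaging at screening, and its footnote says: "Screening period is a total of 28 days".

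Section 9.1.2 names the Kaplan-Meier method for overall survival and RFS only. No section gives DMFS an estimation method, a censoring rule, a delayed-entry adjustment or a competing-risk treatment.

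**The concern.** A patient found to have metastases, or who dies, between surgery and the eligibility scan cannot be in the data set. Everyone analysed has passed through that interval without an event by design. A curve that starts at surgery and counts all patients as at risk from day zero credits the interval to DMFS as event-free follow-up. With a single arm there is no control group in which the same credit would cancel.

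The second problem is death. On one clock, with death as an event, DMFS can never exceed overall survival. With metastasis as the only event and deaths censored, that ordering is lost. A patient who dies without a recorded metastasis then contributes no DMFS event.

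At stake is a named secondary endpoint that would look better than it should, on a different clock from the two endpoints reported beside it.

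**Working it through.** The plan gives no DMFS rate, median or sample size, so there is no DMFS figure to reproduce. Its sample size (63 evaluable, 73 enrolled, section 9.3) is built on 24-month RFS and does not involve DMFS.

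**Inputs from the documents**

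- Ceiling on the gap from sentinel node surgery to first dose: 120 days, or 120/30.4375 = 3.9 months (section 4.1.1, item 12).
- Imaging can precede first dose by up to 28 days (section 6.1). At the 120-day ceiling, the time guaranteed by the scan is therefore between 120 − 28 = 92 days (3.0 months) and 120 days (3.9 months).
- Follow-up: 48 months (section 3.5), or visits through month 60 of the study (section 7.1).

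**Assumptions (not in the documents)**

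- Constant hazard.
- 24-month freedom from distant metastasis, S, of 80% or 85% from first dose.
- For the second step only, deaths without metastasis at 1% per year.

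**Step 1: time origin alone.** With a guaranteed event-free gap of d months, the 24-month mark from surgery reflects only 24 − d months at risk, so the reading is S^((24 − d)/24).

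| Gap d (months) | True 85% reads | Excess (points) | True 80% reads | Excess (points) |
|---|---|---|---|---|
| 1 | 85.6% | 0.6 | 80.7% | 0.7 |
| 2 | 86.2% | 1.2 | 81.5% | 1.5 |
| 3 | 86.7% | 1.7 | 82.3% | 2.3 |
| 4 | 87.3% | 2.3 | 83.0% | 3.0 |

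The 3- and 4-month rows bracket the 92- and 120-day cases at the ceiling.

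**Step 2: adding the omission of death.** Take S = 85%, d = 3.9 months and 1% deaths per year.

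- As defined, with deaths censored: 0.85^((24 − 3.94)/24) = 0.873.
- From first dose, with death as an event: 0.85 × 0.99² = 0.833.
- Difference: 4.0 points, of which 0.873 − 0.850 = 2.3 come from the origin and 0.850 − 0.833 = 1.7 from the deaths.
- With S = 80%: 0.830 against 0.80 × 0.99² = 0.784, a difference of 4.6 points.
- With no deaths without metastasis, only the excess in step 1 remains.

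**Step 3: the median.** Under the same model the median from first dose is 24 × ln 2 / (−ln S): 102 months at 85% and 75 months at 80%. Timing from surgery lengthens either one by d. Both exceed 48 and 60 months, so the planned median would probably not be reached. The bias would then show mainly in the curve and in any percentage read from it.

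**The case against.** The best defence is that the plan under-specifies DMFS rather than prescribing a biased analysis. It names no method and no censoring rule, so both a Kaplan-Meier curve from surgery and the censoring of deaths are inferred. That is fair on method. It does not rescue the definition: surgery is stated as the origin, metastasis is the only stated event, and nothing elsewhere adds delayed entry. Censoring deaths is what that definition leads to by default.

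It is also fair that the effect is modest. DMFS has no hypothesis, threshold or test. The listed objective is a median that will probably not be reached, and no 24-month DMFS rate is listed. At 85% with 63 patients, a simple 90% binomial interval is ±1.645 × √(0.85 × 0.15/63) = ±7.4 points, wider than the shift. This limits severity. But the shift runs one way and a larger sample would not remove it.

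Four stronger readings are tempting, and the documents do not support them:

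- **That every patient carries months of guaranteed time.** The 120 days is a ceiling with no minimum, some patients may start within weeks, and the plan does not define definitive surgery.
- **That the gap reaches six months.** That limit runs from initial diagnosis, not from surgery.
- **That nodal metastases would count because the definition ends at metastatic disease without qualification.** The term being defined is distant metastases-free survival, and the entry criteria use the same words for what systemic imaging must exclude. Counting nodal events would in any case lower DMFS.
- **That the result could not be fairly compared with any external series.** The documents give no time origin for any external DMFS series.

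Finally, the omission of death is not peculiar to DMFS. Section 9.1.2 leaves it out of RFS too, against section 2.2, and the two sections also disagree on the RFS origin.

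**Conclusion.** The definition is wrong as written, and the direction of the origin bias is clear: without delayed entry, the interval from surgery to the eligibility scan pushes DMFS up. Under a constant hazard and an assumed true 24-month DMFS of 80-85% from first dose, the origin adds 1.7 to 3.0 points when the gap is 3 to 4 months, and 0.6 to 1.5 points when it is 1 to 2 months. Any median is lengthened by the gap itself. If deaths are censored, the excess grows by an amount that depends on a death rate the documents do not give; at an assumed 1% per year it reaches 4.0 to 4.6 points at the 120-day ceiling.

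Severity is moderate. A reader might infer that the trial's main conclusion is at risk, but the primary endpoint, its test and the 63/73 sample size do not use DMFS.

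**What to change.** Reconcile the RFS definitions in sections 2.2 and 9.1.2 first, so that the trial has one time origin and one rule on death. Then define DMFS from first nivolumab dose, or from that single origin, to first distant metastasis or death from any cause. Patients without an event are censored at their last disease assessment. Add DMFS to the endpoints estimated by Kaplan-Meier.

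If surgery is kept as the origin, define definitive surgery and let each patient join the risk set only at first dose (delayed entry). If death is not to be an event, report the cumulative incidence of distant metastasis with death as a competing risk.

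The change is wording only, and should be fixed before results are seen. The cost is a slightly less favourable reported DMFS. The delayed-entry version also has small risk sets soon after surgery, so the start of that curve would be less stable.

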### **9.2. Interim Analyses and Stopping Rules**

The Principal Investigators and coordinators will have monthly conference calls to review study data and subject safety issues. Decisions to continue or close the trial to accrual and subject recruitment, accrual and retention, and/or if the trial should continue are also discussed during these meetings. Any modifications necessary to ensure subject safety are discussed and modifications will be submitted to the IRB. If any literature becomes available which suggests that conducting this trial is no longer ethical, the study will be terminated and the IRB will be notified of the new findings. The IRB will be notified of any change in the risk/benefit ratio that would affect whether the study should continue.

### **9.3. Sample Size Considerations**

Based upon recent retrospective analyses, the 24 month recurrence free survival rate for our patient population is 70%. To demonstrate a 50% improvement in the 24 month recurrence free survival rate (0.70 vs 0.85), with power of 0.90, alpha 0.05 using one arm non-parametric survival (one-sided) test, we will require enrollment of 63 evaluable patients. To account for potential loss to follow up of 15%, our target number of enrolled subjects is 73. We will require 24 months of follow-up for all patients for evaluation of the primary endpoint.

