## Protocol Synopsis

Protocol Title:	Adjuvant Nivolumab in Patients with Resected Stage IIB/IIC Melanoma
Site Number and Names:	Sidney Kimmel Cancer Center, Thomas Jefferson University Columbia University Medical Center Cancer Institute of New Jersey Fox Chase Cancer Center University of Pennsylvania
Research Hypothesis:	Nivolumab administered in the adjuvant setting will improve clinical outcomes in patients with resected American Joint Committee on Cancer stage IIB or IIC cutaneous melanoma (eighth edition.)
Study Schema: (Drugs/ Doses/ Length of Treatment)	We will enroll approximately 63 evaluable subjects with resected stage IIB or stage IIC cutaneous melanoma in this multicenter single arm phase II clinical trial. All eligible patients will receive 48 weeks of nivolumab 480 mg IV every four weeks for 48 weeks. Patients will be followed for disease recurrence and overall survival.
Study Objectives:	
Primary endpoint:
 
 
Recurrence-free survival rate at 24 months.
 
 
Secondary endpoints:
 
 
To evaluate and estimate the median duration of overall survival (OS) in Stage IIB-IIC melanoma patients.
 
To evaluate and estimate the median duration of distant metastases-free survival (DMFS) in Stage IIB-IIC melanoma patients.
 
To assess safety and toxicity using CTCAE V5.0
 
To assess quality of life using the Functional Assessment of Cancer Therapy – Melanoma (FACT-M) quality of life instrument
 
 
Exploratory Objectives
 
 
To assess and compare clinical, histological, immunological and molecular panels as prognostic and predictive biomarkers.
 

Study Type:	Multicenter single arm phase II clinical trial
Accrual Goal: (Total number of patients)	We will require enrollment of 63 evaluable patients. To account for a potential loss to follow up rate of 15%, our target total number of enrolled subjects is 73.
Accrual Rate:	We anticipate an accrual of 3-4 patients per month once all participating centers are activated.

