## Schematic of Study Design:

## 1. INTRODUCTION

### 1.1 Research Hypothesis

Newer immunotherapeutic agents such as nivolumab, though not without side effects, possess a better safety profile than ipilimumab and high dose IFN- $\alpha$ , with greater efficacy in the metastatic setting. We theorize that adjuvant nivolumab therapy for melanoma patients with IIB-IIC disease may result in improved clinical outcome in this group of patients. Our hypothesis is that 48 weeks of adjuvant nivolumab in stage IIB-IIC cutaneous melanoma will improve the recurrence-free survival (RFS) rate at 24 months from 70% to 85% (50% improve in RFS.)

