## **9. STATISTICAL CONSIDERATIONS**

### **9.1. Analysis Plan**

#### **9.1.1. Baseline Characteristics**

Baseline descriptive statistics on all evaluable patients will be provided on demographic variables (age, sex, and race/ethnicity), performance status, laboratory parameters, the treatment regimens that were previously used, and disease characteristics.

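### Enrolling 73 allows for 13.7% loss rather than the stated 15% (75 would be needed), and moving RFS from 0.70 to 0.85 is not a 50% improvement in the RFS rate; both are small corrections of stated figures

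*Combined protocol and SAP*

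**What the plan says.** Section 9.3 sizes a single-arm comparison of 24-month RFS: "To demonstrate a 50% improvement in the 24 month recurrence free survival rate (0.70 vs 0.85), with power of 0.90". It sets a one-sided alpha of 0.05, names a one-arm non-parametric survival test, and arrives at 63 evaluable patients. It then adds: "To account for potential loss to follow up of 15%, our target number of enrolled subjects is 73". Section 3.3 gives the same three figures, and the Synopsis repeats them: "To account for a potential loss to follow up rate of 15%, our target total number of enrolled subjects is 73".

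The hypothesis in Section 1.1 describes the same effect as raising the RFS "rate at 24 months from 70% to 85% (50% improve in RFS".

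On who is analysed, Section 9.1.1 says "Baseline descriptive statistics on all evaluable patients will be provided". Section 9.1.2 says that RFS will be estimated by Kaplan-Meier and does not restrict the patients. Section 9.3 asks for 24 months of follow-up on everyone for the primary endpoint. The word *evaluable* is not defined anywhere.

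**The concern.** Three statements in the sizing text do not fit together as written.

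- **Inflation.** An allowance for loss should leave the required number after the loss has occurred. The plan appears to add 15% to 63 instead of dividing 63 by the fraction retained.
- **Effect label.** A 50% improvement on a rate of 0.70 would be 1.05, which is impossible. The label must refer to something other than the RFS rate.
- **Evaluable.** The size is expressed in a population that the plan does not define, so a reader cannot tell how patients lost before 24 months enter the primary test.

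At stake are the accuracy of the stated loss allowance, a reader's understanding of the size of effect sought, and the power that can be quoted for the primary test.

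**Working it through.** **Inputs.** Section 9.3 gives null RFS p0 = 0.70, alternative p1 = 0.85, one-sided alpha 0.05 (z = 1.645), power 0.90 (z = 1.282), 63 evaluable patients, 15% loss and 73 enrolled.

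**1. The plan's 63.** I took a one-sample test of 24-month RFS with no censoring before 24 months. The normal approximation is

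n = (1.645·√(0.70·0.30) + 1.282·√(0.85·0.15))² / 0.15² = (0.754 + 0.458)² / 0.0225 ≈ 65.2.

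The other usual scales give 64.7 (arcsine), 64.9 (log-log) and 65.5 (logit). The plan's 63 is therefore 2 or 3 patients below these results once they are rounded up. That is ordinary variation between formulas.

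**2. The plan's 73.** 63 × 1.15 = 72.45, which rounds up to 73 and reproduces the stated target.

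**3. The correct inflation.**

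- Needed for 15% loss: 63 / (1 − 0.15) = 74.1, so 75. (74 × 0.85 = 62.9; 75 × 0.85 = 63.75.)
- Left from 73 at 15% loss: 73 × 0.85 = 62.05.
- Loss that 73 can absorb: (73 − 63)/73 = 13.7%.

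**4. What one patient costs.**

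| Method | Power at 63 | Power at 62 |
|---|---|---|
| Normal | 88.9% | 88.4% |
| Logit | 89.1% | 88.7% |
| Arcsine | 89.3% | 88.9% |
| Log-log | 89.4% | 89.0% |
| Exact binomial | 85.8% (at least 51 event-free; alpha 0.035) | 87.1% (at least 50; alpha 0.041) |

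The first four rows are large-sample formulas and fall by 0.4 to 0.5 point. The exact row moves the other way because its cut-off is a whole number. Its lower level is already present at 63 and is not caused by the inflation.

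**5. The effect label.**

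- Relative rise in RFS: 0.85/0.70 − 1 = 21.4%.
- Relative fall in 24-month events: 1 − 0.15/0.30 = 50%.
- Hazard ratio, assuming exponential survival: ln 0.85 / ln 0.70 = 0.456.

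The sample size uses 0.70 and 0.85 directly, so the label does not alter it.

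**6. Power with losses censored.** These are simulations of 20,000 trials with 73 treated patients and exponential event and loss times. The loss is assumed to be random and to reach 15% by 24 months. The test is made on the 24-month Kaplan-Meier estimate.

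| Test | Power at true RFS 85% | One-sided error at true RFS 70% |
|---|---|---|
| Log-log | about 89% | about 4% |
| Arcsine | about 92% | about 5.6% |

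The mean Kaplan-Meier estimate at a true RFS of 85% is 85.0%.

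**7. A conditional check on *evaluable*.** Suppose that the word meant dropping event-free patients lost before 24 months while keeping everyone who recurred earlier. In the same simulations, a mean of 62.9 patients would remain, mean RFS would be about 84%, and power would be about 80 to 85% depending on the test.

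**The case against.** The strongest reply is that all of this is clerical. Loss of 15% is itself a planning guess, 73 and 75 differ by two patients, and the power cost is about half a point. The rates 0.70 and 0.85 are printed beside the 50% label, so nobody would size the trial wrongly from it. All of that stands and limits the weight of the point. It does not make the stated loss allowance or the label correct.

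A reader might infer more: that the design misses its 90% power because the analysis is confined to evaluable patients. The documents do not support this. Section 9.3 names a survival test, Section 9.1.2 names Kaplan-Meier without restricting the patients, and Section 7.2 keeps those who stop drug in follow-up unless they withdraw consent for contact. Nothing says that event-free patients who are lost are to be dropped. That reading would also leave a mean of 62.9 patients rather than 62, because it keeps early recurrences. The shortfall in step 3 and the power loss in step 7 therefore rest on different definitions and should not be added together.

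A reader might equally infer that censoring the losses secures the stated 90% at 5%. That is not shown either. Log-log stays slightly below 90%, and arcsine passes it with an error slightly above 5%.

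**Conclusion.** Two stated figures are wrong. The enrolment target of 73 allows for 13.7% loss, and the 15% claimed would need 75. The effect is a 21% relative rise in RFS or a 50% reduction in 24-month events, not a 50% improvement in the RFS rate. The first costs about one evaluable patient and 0.4 to 0.5 point of power on the standard formulas; the second changes no calculation.

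The undefined term *evaluable* is an ambiguity to close and not a demonstrated loss of power. The fall to about 80 to 85% arises only under the reading in step 7, which the plan does not mandate. The simulated figures also rest on exponential times and on 15% loss unrelated to outcome, neither of which the documents state. The inflation and effect-label arithmetic needs neither assumption, apart from the hazard ratio, which takes survival as exponential.

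**What to change.** 1. **Synopsis, 3.3 and 9.3:** keep 73 and state that it yields 63 evaluable patients with up to 13.7% loss. If the 15% allowance is to be kept instead, the target is 75.
2. **1.1 and 9.3:** describe the effect as a 50% reduction in recurrence or death by 24 months (30% to 15%), with a hazard ratio of about 0.46 under exponential survival.
3. **9.1.2 and 9.3:** state that the primary test uses the 24-month Kaplan-Meier estimate in all treated patients, with those lost censored at their last disease assessment. Define *evaluable*, or remove it from the sizing text and from 9.1.1.
4. **9.3:** name the exact test and quote its power and one-sided error together. With 73 treated and an assumed 15% random loss, these are about 89% and 4% for log-log, or about 92% and 5.6% for arcsine.

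The cost is wording in five places. No extra patients are needed if 73 is kept, and two if 15% is retained.
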